Our objective is to determine the effect of and compare two different doses of IV dexamethasone given preoperatively before TKA, when compared to placebo, using the outcome measures listed below:

Primary Outcome Measures

- To assess patient reported visual analog pain scores.
- To assess patient controlled analgesic usage.

Secondary Outcome Measures

1. To assess the soft tissue swelling about the operative knee after steroid administration.
2. To assess postoperative glucose levels after steroid administration.
3. To assess rehabilitation parameters such as postoperative knee range of motion and time to physical therapy clearance.
4. To assess incidence of nausea and vomiting postoperatively after steroid administration.
5. To assess patient satisfaction and function scores at 4 months with both Short Form (SF) – 12 and Knee Injury and Osteoarthritis Outcome Score Short Form (KOOS, Jr.) scores.
6. To assess hospital admission characteristics such as length of stay and rate of readmission.
7. To assess the risk of infection at 4 months and wound drainage at 7 days after perioperative steroid administration in total knee arthroplasty.

Study Design and Methods

We plan to conduct a prospective, double-blinded, randomized, placebo-controlled trial to evaluate perioperative glucocorticoid administration in total knee arthroplasty. There will be three arms in the study: 1) Placebo, 2) 10 mg dexamethasone, and 3) 20 mg dexamethasone.

Consent to Participation in the Study

Patients will be given the opportunity to participate in the study at the time of consent for surgery and blood product, which typically takes place in clinic during an evaluation for severe end-stage arthritis. It will be emphasized that study participation is optional, and that patients may be randomized to the control or placebo group. Patients will sign the combined informed consent and HIPAA form in order to participate in the study.

Method of Randomization

Once a patient chooses to be part of the study, he/she will be randomized in a blocked fashion to either the control group or to one of two intervention groups. Randomization will occur after informed consent has been obtained from the patients and after the preoperative screening examination is complete. Patients and investigators will be blinded to the randomization assignment. Emory's Investigational Drug Services will randomize each patient prior to dispensing the blinded dexamethasone/placebo doses.

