
Data Collection

Data will be collected by a number of different health professionals during enrollment, during the patient's postoperative hospital stay, by smart device application (app), and during the patient's routine postoperative follow up visits (1 month, 4 months, and 12 months). After surgery, no participants in any group will be subjected to any extra invasive tests or interventions related to their involvement in the study. Patients will not be informed whether or not they have received the study

drug until after all data collection is complete. The schedule of study activities and data collection are shown in Table 1.

1. **Pain assessment:** Postoperative pain will be assessed using the well-standardized and accepted visual analog pain scale. This data will be recorded at baseline, during the hospital stay, and at all follow-up visits. A smart device app will be used to record this information for the 7-day postoperative period. Questions will be asked morning, afternoon, and evening for every patient. Patients enter alarms for morning, afternoon, and evening the first time they use the app. Patients can later adjust these alarms if necessary. Timestamps will be recorded for each of these entries as patients will be asked about their 'average' pain over the preceding 4 hours, and they will be able to edit/modify prior entries at any time. Patients will also be asked during the first entry for the day if they were awoken from pain or nausea during the previous night, and if they click yes, they will be prompted to select pain scores corresponding to this event. There will be a comments section to provide patients the ability to enter text. Furthermore, during the hospital stay this data will be recorded with each vital sign assessment by the nursing per standard of care. The following scale will be used to assess pain:

[figure not shown]
©1983 Wong-Baker FACES® Foundation. www.WongBakerFACES.org
Used with permission.

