7. **Blood Glucose Levels:** The patient's blood glucose level will be recorded once preoperatively at the pre-anesthesia clinic visit several days before surgery, at POD 1 and at each subsequent in-hospital POD using a hemocue. These do not consist of extra blood tests, as blood draws at these time points are considered standard of care. This data is being collected because hyperglycemia is a potential complication of IV steroid use. If patients experience ketoacidosis or hyperglycemia greater than 300, the study drug/placebo will be discontinued.
8. **Functionality scores:** The Short Form (SF) – 12 and Knee Injury and Osteoarthritis Outcome Score Short Form (KOOS, Jr.) questionnaires will be administered to patients at the baseline visit and at each follow up clinic visit. Both of these standardized function questionnaires are well validated and widely accepted in the literature.
9. **Hospital length of stay and readmission:** We will record the length of each patient's hospital stay and any readmission to our hospital for the 12-month duration of study.
10. **Infection:** Patients will have standard follow up clinic appointments at 1 and 4 months after surgery, at which time the clinical presence of possible wound drainage and periprosthetic infection will be evaluated. Patients will be followed up to 1 year after surgery to monitor for latent infections.

Table 1: Outcome measure and data collection schedule

	Pre-operative clinic visit	Each inpatient day	7 day app usage	2 week app usage	1 month clinic visit	4 month clinic visit	12 month clinic visit
Consent, Enrollment, Randomization	X						
Pain assessment	X	X	X		X	X	X
Opioid usage		X					
Pain medication log			X	X			
Knee swelling	X	X			X	X	
Knee ROM	X	X			X	X	X
Physical therapy milestones		X					
Nausea/vomiting		X	X				
Blood glucose	X	X					
Postoperative infection/Wound drainage		X			X	X	X
Length of stay		X					
KOOS, Jr. and SF-12	X				X	X	X

Consent Process

Patients will be asked to participate in the study at a preoperative clinic visit. The risks, benefits and the optional nature of the study will be emphasized. Patients may withdraw from the study at any given time. Consent will be obtained from one or more of the following three people: the attending surgeon, the orthopaedic surgery resident, or the research coordinator.

Participant Selection

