After the study is complete, statistical analysis will be performed using de-identified patient data to determine differences in primary and secondary outcomes. Repeated-measures analyses for VAS pain score (and change from baseline), knee ROM, functionality scores (SF-12 and KOOS, Jr.), and blood glucose will be done with a means model with SAS Proc Mixed (version 9, mixed linear models) providing separate estimates of the means by time on study (baseline, in hospital, day 7, and at 1,4 and 12 months after total knee arthroplasty) and treatment group (dexamethasone or control). A compound symmetry variance-covariance form among the repeated measurements will be assumed for each outcome and robust estimates of the standard errors of parameters will be used to perform statistical tests and construct 95% confidence intervals²⁶. T-tests will be used to compare the pairwise differences between the model-based treatment means (least-squares means) at each time point. Mean changes over time within a treatment group will be tested for linear trend. The model-based means are unbiased with unbalanced and missing data, so long as the missing data are non-informative (missing at random). A

dropout process is assumed to be missing at random if, conditional on the observed data, the dropout is independent of the unobserved measurements. Statistical tests will be two-sided. A p value < 0.05 will be considered statistically significant.

Adverse Event Reporting

At a six-month time point following initiation of the study, we will assess our results for any reportable adverse events, including postoperative infections. This data will be reported to the Emory Institutional Review Board (IRB). We will monitor for any adverse outcomes at each subsequent six-month interval.

Data Safety and Monitoring Plan

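### The two first-week levels in the primary pain model, 'in hospital' and 'day 7', either leave post-discharge app scores without a level or cover the same days twice; postoperative days 1 to 7 would avoid both

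*Combined protocol and SAP*

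**What the plan says.** Pain is the first listed primary outcome (Objectives): "To assess patient reported visual analog pain scores".

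Data Collection, item 1, sets up two streams of postoperative pain scores in the first week:

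- **App:** "A smart device app will be used to record this information for the 7-day postoperative period". On the frequency of prompts, the same item states: "Questions will be asked morning, afternoon, and evening for every patient".
- **Nursing record:** "during the hospital stay this data will be recorded with each vital sign assessment by the nursing per standard of care".

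App pain entry does not depend on discharge. The opioid item, by contrast, moves to the app only once the patient has gone home.

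In Table 1 the pain row is marked under six columns: the pre-operative visit, each inpatient day, the column headed "7 day app usage", and the 1, 4 and 12 month visits.

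Statistical Analysis describes one method for pain, shared with three other groups of outcomes: "Repeated-measures analyses for VAS pain score (and change from baseline), knee ROM, functionality scores (SF-12 and KOOS, Jr.), and blood glucose". The model estimates "means by time on study (baseline, in hospital, day 7, and at 1,4 and 12 months after total knee arthroplasty". Arms are compared with t-tests that "compare the pairwise differences between the model-based treatment means (least-squares means) at each time point". No area under the curve, weekly mean or daily profile is described. Nor is there a rule for reducing the several scores in a day or a stay to the value for a level.

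**The concern.** A repeated-measures means model needs time levels that do not overlap and that mean the same thing in each arm. For the first week of pain scores, the two named levels do not meet that need on either available reading.

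- If 'day 7' is the seventh day, scores entered at home before it belong to no level. The early post-discharge difference between arms then cannot be estimated, although the app collects the data for it.
- If 'day 7' is the whole week of app use, it includes the days in hospital. Two levels that share days are then treated as separate time points.
- On both readings, 'in hospital' ends at discharge. Length of stay is a secondary outcome, and the Introduction reports that an earlier randomised dexamethasone trial found shorter stays. If that recurs, the 'in hospital' contrast compares different sets of postoperative days between arms.

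Pain is also the outcome on which the trial was sized, so its first-week comparison should not rest on an undefined label.

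**Working it through.** The plan gives no figure on this point to reproduce. The check is a count of scheduled scores and a comparison of sections.

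**Inputs from the documents.** 3 app prompts per day and 7 days (Data Collection, item 1); two first-week levels (Statistical Analysis); six columns marked for pain (Table 1).

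**Assumptions.** The app week is POD 1 to 7. The whole day of discharge counts as in hospital. The day of discharge, POD d, is varied because the documents give no length of stay.

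**Scheduled scores.** 7 × 3 = 21 per patient.

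**Reading 1: 'day 7' is a single day.** The days with no level run from POD d + 1 to POD 6, which is 6 − d days or 3 × (6 − d) scores.

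**Reading 2: 'day 7' is the app week.** The week shares d days with 'in hospital', on which 3 × d app prompts fall.

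| Discharge | Reading 1: scores with no level | Share of 21 | Reading 2: app prompts on shared days |
|---|---|---|---|
| POD 1 | 15 | 71% | 3 |
| POD 2 | 12 | 57% | 6 |
| POD 3 | 9 | 43% | 9 |
| POD 4 | 6 | 29% | 12 |
| POD 5 | 3 | 14% | 15 |
| POD 6 | 0 | 0% | 18 |

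No discharge day clears both columns. The earlier the discharge, the more scores lack a level on reading 1; the later the discharge, the greater the overlap on reading 2.

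**Dependence on length of stay (both readings).** Suppose daily mean pain is the same in two arms, m1, m2 and m3 on POD 1 to 3, so that there is no effect on pain. Let one arm leave on POD 3 and the other on POD 2, and let 'in hospital' be a simple average over the stay. The difference between arms is

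(m1 + m2 + m3)/3 − (m1 + m2)/2 = [m3 − (m1 + m2)/2]/3.

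This is zero only if POD 3 pain equals the average of the two days before it. A shift in discharge alone can therefore produce a pain contrast at this level. Its size cannot be given, because the documents contain no daily pain means.

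**Number of contrasts.** As written there are 5 post-baseline levels and 3 pairs of arms: 5 × 3 = 15 tests. With seven daily levels and three visits there are 10 × 3 = 30. The fix must deal with this increase.

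**The case against.** The strongest reply is that the list of time points is shorthand. Its six labels match, in order, the six Table 1 columns marked for pain, so 'day 7' stands where the week of app use stands. The same list serves range of motion, function scores and glucose, none of which has a scheduled day 7 measurement. The same sentence also names two treatment groups for a three-arm trial. This stands in part. A reader might infer that the post-discharge app scores are discarded, but the documents nowhere say so; it follows only from the literal reading. The Table 1 reading does not rescue the levels, however, because a seven-day postoperative window contains the inpatient days.

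A second reply is that 'in hospital' may use the nursing record and 'day 7' the app, so that no score is counted twice. That is possible, and the documents do not establish double counting of individual scores. The two levels would still describe overlapping days, and the plan does not say which source feeds which level.

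A third reply concerns the remedy. App-only daily means leave nurse-recorded scores out of the main comparison, daily levels double the number of contrasts, and a weekly average dilutes an effect that fades. All three are fair, and the fix answers them.

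**Conclusion.** The point holds as a defect in the first-week time levels for the primary pain outcome. On the literal reading, 43% to 71% of scheduled app scores have no level if discharge is on POD 1 to 3, falling to 29%, 14% and 0% for POD 4, 5 and 6. On the Table 1 reading nothing need be lost, but 'in hospital' and 'day 7' are not distinct time points. On both, the span of 'in hospital' depends on length of stay. The percentages rest on an assumed discharge day; the overlap and the dependence on stay do not need a particular one.

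Two stronger conclusions are tempting, and the documents do not support them.

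- A reader might infer that the scores without a level are those nearest the study doses. Therapeutic Intervention puts the first dose before surgery and the second eight hours later in the inpatient setting. The nearest days are therefore inpatient days, which the model keeps.
- A reader might infer a sample-size equivalent of the lost precision. The sample-size paragraph gives neither the SD nor the time point behind 47 per arm, 'in hospital' is already built from several scores, and any such conversion needs a constant effect over the week. Nothing here shows that 47 per arm is wrong.

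The change should be made before the analysis. It is more than a request for definitions, because fixed postoperative days work under either reading with data already being collected.

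**What to change.** For VAS pain only, amend Statistical Analysis as follows:

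1. Replace 'in hospital' and 'day 7' with POD 1, 2, 3, 4, 5, 6 and 7. Keep baseline and 1, 4 and 12 months.
2. Define each daily value as the mean of that day's scheduled app scores, whether the patient is in hospital or at home, and state how a day with missing entries is handled.
3. Base the first-week comparison between arms on one pre-stated average of the seven daily means. Report day-by-day contrasts as supportive.
4. Report nurse-recorded inpatient scores separately, including those from the day of surgery.

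**Cost.** Plan wording and a few lines of code, with no new data and no more patients. The post-baseline pairwise contrasts rise from 15 to 30; the single pre-stated average keeps the first-week conclusion from depending on the best-looking day. If the effect fades within the week the average will be somewhat diluted, and the daily estimates will show it.

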This study will be conducted at Emory University Orthopaedic and Spine Hospital and Clinic. The investigators perform over 500 total knee arthroplasty procedures per year. We estimate 75% (375) of the patients will be eligible and be willing to participate in the study. The Department of Orthopaedics staff performs 10-20 clinical trials per year and therefore is well-trained and prepared to perform clinical trials of this magnitude.

Inclusion Criteria

1. Patients undergoing primary total joint arthroplasty of the knee
2. Adult patients ages 18-100 years
3. Patients must have smart phone and/or device for app usage

Exclusion Criteria

1. Current chronic steroid use
2. Patients undergoing revision knee surgery
3. Patients ambulating preoperatively with assistive devices
4. Patients with avascular necrosis of the operative knee
5. Patients with a history of an adverse reaction to glucocorticoid steroids
6. Patients unable to provide informed consent
7. Patients with inflammatory arthritis
8. Prisoners
9. Current smokers
10. Patients <18 years of age
11. Any patient with a complicated postoperative course that requires transfer to the Intensive Care Unit (ICU) or to another facility for further management will be removed from the study.
12. Any contraindication that would prevent the patient from being treated with the standard multimodal postoperative pain management regimen
13. History of infection of surgical knee.
14. Patients with diabetes.
15. Patients that have an intolerance to Toradol.
16. Patients that do not have smart phone and/or device for app usage

Statistical Analysis

In order to adequately examine our primary outcome measure of pain reduction, our target sample size was obtained by a power analysis using retrospective data. Assuming a mean difference in the VAS of 1.5 between placebo vs. low dose and 1.5 for low dose vs. high dose (or 3 between placebo and high dose), in order to achieve 90% power, we will need 47 patients per study arm. Thus, the total number of patients enrolled would need to be at least 141. Based upon historical data, we expect it to take 18 months to reach our target N of 141.

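### No time point or window is designated for the primary pain outcome, and the second primary, worded as patient-controlled analgesia, does not match the opioid data collected and has no named model

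*Combined protocol and SAP*

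**What the plan says.** **Pain.** Primary Outcome Measures lists VAS pain scores with no time, window or summary. The sample-size paragraph of Statistical Analysis speaks of "our primary outcome measure of pain reduction" and continues "Assuming a mean difference in the VAS of 1.5 between placebo vs. low dose", again without saying when. The analysis paragraph gives separate means by arm at "baseline, in hospital, day 7, and at 1,4 and 12 months after total knee arthroplasty". It then states: "T-tests will be used to compare the pairwise differences between the model-based treatment means (least-squares means) at each time point". The threshold follows: "A p value < 0.05 will be considered statistically significant". No level is ranked first and no adjustment is described.

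Data Collection item 1 takes in-hospital pain from two sources: nursing vital-sign checks, and app questions three times a day for seven days. The Table 1 column is "Each inpatient day", whereas the analysis paragraph has a single in-hospital label.

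**Opioids.** Primary Outcome Measures words the second primary as patient-controlled analgesic use. Therapeutic Intervention lists morphine PCA only for patients in whom the other agents fail. Data Collection item 2 records all inpatient opioid use in morphine equivalents per day, then an app count of pills per day, up to two weeks. Table 1 separates these: opioid usage is ticked for inpatient days only, and a different row, "Pain medication log", covers the app periods. The named models are "Repeated-measures analyses for VAS pain score (and change from baseline), knee ROM, functionality scores (SF-12 and KOOS, Jr.), and blood glucose". Opioid use is not among them, although the paragraph opens with a general commitment to analyse primary and secondary outcomes.

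**The concern.** A primary outcome has to identify the one comparison that decides it. Here several pain comparisons, from the hospital stay to one year, have equal standing, and the power statement belongs to none of them. Whoever reports the trial could present whichever level reached significance as the primary result without departing from the text.

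The second primary has a different fault. Its wording points to a rescue modality that some patients may never receive, while the data describe total opioid use. Someone must decide which quantity is meant, over which days and with which model, and the plan leaves those decisions until after the data are in.

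The omission is not the protocol's general style. Among the secondary outcomes, function scores and infection are fixed at 4 months and wound drainage at 7 days.

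**Working it through.** **1. The plan's own figure.** Inputs from Statistical Analysis: difference 1.5, power 90%, two-sided 0.05, 47 per arm; 3 × 47 = 141, as stated. No SD is given, so 47 cannot be reproduced forwards. Solving backwards for a two-arm comparison (normal approximation):

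SD = 1.5 / [(1.960 + 1.282) × √(2/47)] = 1.5 / (3.242 × 0.2063) = 2.24.

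A three-group F test with means 0, 1.5 and 3 would instead imply an SD of 4.04. The documents do not say which calculation was used, or which pain measure and time the retrospective data describe. This matters because the SD may differ by time and by summary. For a difference of 1.5:

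| Assumed SD | Needed per arm for 90% power | Power with 47 per arm |
|---|---|---|
| 2.0 | 38 | 95% |
| 2.24 | 47 | 90% |
| 2.5 | 59 | 83% |
| 3.0 | 85 | 68% |

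**2. Exposure from an undesignated time.** Count of post-baseline levels: in hospital, day 7, and 1, 4 and 12 months, so five. There are more if the in-hospital label means one level per inpatient day. Take one dose-versus-placebo contrast with no true effect, each level tested at 0.05, and suppose that significance at any level is read as success.

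- Independent levels: 1 − 0.95⁵ = 0.226.
- Correlated levels: simulate Z_k = √ρ·U + √(1−ρ)·E_k, with U and E_k standard normal, and count trials with any |Z_k| > 1.96 (400,000 null trials per setting). This is the compound-symmetry structure that the plan itself assumes. The values of ρ are my assumption, since the documents give none.

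| ρ | Five levels | Seven levels (three inpatient days, assumed) |
|---|---|---|
| 0 | 23% | 30% |
| 0.3 | 21% | 27% |
| 0.5 | 18% | 23% |
| 0.7 | 15% | 18% |
| 0.9 | 10% | 11% |

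Counting all three arm pairs over five levels (15 tests) gives about 48% at ρ = 0 and 32% at ρ = 0.7. Three pairs at one named time give about 12%, so part of that larger figure comes from having three arms, not from the missing time point. The single-contrast column isolates the time-point issue.

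**3. The second primary, place by place.** No arithmetic applies.

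- Primary Outcome Measures: patient-controlled analgesic use; no unit or window.
- Therapeutic Intervention: PCA only after failure of the other listed agents.
- Data Collection item 2, in hospital: all opioids, morphine equivalents per day.
- Data Collection item 2, after discharge: pills per day from a preloaded list; no conversion stated.
- Statistical Analysis: the power paragraph treats pain as the only primary, and no opioid model is listed.

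Inpatient morphine equivalents are the best-supported reading of what was meant, but that is not what the outcome says.

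**The case against.** **The mixed model uses every time point.** It estimates each mean, but it does not say which test decides the primary outcome. Nor does the seven-day app period settle this: it is a collection window and is never called primary.

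**The plan never says that any significant level counts as success.** This stands. The percentages are conditional on that reading and on assumed correlations. A reader might infer that the trial has a 15–23% type I error rate; the documents do not support that.

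**The opioid outcome is better defined than it looks.** Largely fair. Data Collection item 2 gives the inpatient quantity and unit, the analysis paragraph commits generally to analysing the primary outcomes, and patient-controlled could loosely mean as-needed use. So the outcome is not beyond analysis. What remains missing is matching wording, a window and a model.

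Three further inferences go beyond the text:

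- That morphine equivalents over a fixed window running past discharge are already collected. After discharge the stated unit is pills per day.
- That pooling in-hospital scores biases the arms through differing lengths of stay. This would need a pooled level, an effect on stay, a daily pain course and an SD. The documents supply no figures for these, and the direction depends on the assumed course.
- That 47 per arm is wrong. Without the SD it can be neither confirmed nor refuted.

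**Conclusion.** The point holds on the text and should be corrected before the data are analysed. The lack of a designated pain time or window is a matter of reading and needs no assumption. Its possible cost, 15–23% for one contrast over five levels, rests on assumed correlations of 0.7 to 0 and on the any-level reading; at 0.9 it is about 10%, still twice the nominal 5%. The link between the 1.5-point assumption and any particular measure is unknown. The opioid part is a mismatch between the worded outcome, the regimen and the data collected, together with an unnamed window and model. It has no numerical size.

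**What to change.** **Pain.** In Primary Outcome Measures and both paragraphs of Statistical Analysis, name one primary pain measure: one source and one summary, over a window of postoperative days that is the same for every patient regardless of discharge. Make all other time levels secondary, and say whether the in-hospital label is one level or one per inpatient day. The seven-day app scores are one suitable option because they are already collected through discharge. Their drawback is that they are self-reported, may be missing and can be edited later, so the plan should say how such entries are handled. Another single source would also cure the defect.

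**Sample size.** State which measure and time the retrospective data describe, give the SD, and say whether both it and the 1.5-point difference apply to the chosen measure. If they do not, the justification has to be redone, so this is more than rewording.

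**Opioids.** Reconcile Primary Outcome Measures, Therapeutic Intervention, Data Collection item 2, Table 1 and Statistical Analysis so that the second primary is opioid use in morphine equivalents, with inpatient use as the quantity already defined. Name its window and model, and report PCA use separately. If the window runs past discharge, the app log must record drug and strength so that pills can be converted, and a rule is needed for the day of discharge.

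**Cost.** For pain, text and analysis programming, plus the sample-size check. For opioids, the same, and possibly a change to the app list. No extra patient visits or tests are needed.

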Therapeutic Intervention

Patients in the intervention arms will receive two doses of either 10 mg dexamethasone or 20 mg dexamethasone. The first dose will be administered preoperatively within three hours of surgery once the patient receives anesthesia. The second dose will be administered eight hours after the first dose in the inpatient setting by the nurse in that unit. The second dose will be administered using a piggyback setup. Patients in the placebo arm will receive two doses of saline/placebo.

This particular dosing is chosen based on available literature that suggests a safe and effective dose is between 4 and 20 mg of dexamethasone²⁵⁻²⁶.

The administration of either steroid or placebo will occur in a double-blinded fashion. For each study participant, two blinded doses will be sent over from Emory's Investigational Drug Service (IDS). Thus, neither the patient receiving the medication nor the health care professional administering the medication or collecting study outcome data will be aware of whether or not the patient received the steroid or the placebo.

Both the intervention and control groups will receive spinal anesthesia using lidocaine and a standard multimodal postoperative pain management regimen typically used for total knee arthroplasty. This regimen will be standardized across all three attending surgeons participating in the study. The standard multimodal pain management regimen will be as follows:

- Preoperative:
 - **Decadron: 10 or 20mg IV x 2 doses, 8 hours apart (if randomized to study group)**
- Intraoperative:
 - **Ropivacaine:** Given intraoperatively. Injection, subcutaneous tissue/skin. Administered in standard fashion. (300mg)
 - **Toradol:** 30mg q 6hr for 6 total doses. 1st dose given intraoperatively at incision. (15 mg if patient is >65 years of age. Patients with Cr >1.5 will not receive Toradol).
- Postoperative
 - **Tylenol:** 1000mg po q 8hr (scheduled)
 - **Oxycodone:** 5mg or 10mg q 3-4hr prn pain, If intolerant to Oxycodone: second agent line is Hydrocodone or Oral Dilaudid (Tylenol will be adjusted accordingly if patient receives Hydrocodone).
 - **IV Morphine (or Dilaudid):** 1 or 2 mg q 2hr prn breakthrough pain
 - **Morphine PCA:** only for failure of the above
 - **MS Contin:** 15 mg BID for two weeks

On postoperative day (POD) 1, patients will be transitioned to oral (PO) and intravenous (IV) medications on an as-needed basis with a regimen that will be standardized across all study participants.

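### The only analysis model names a two-level treatment factor (dexamethasone or control) in a three-arm dose-comparison trial, so as written it contains none of the three dose contrasts

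*Combined protocol and SAP*

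**What the plan says.** Study Design and Methods: "There will be three arms in the study: 1) Placebo, 2) 10 mg dexamethasone, and 3) 20 mg dexamethasone".

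Objectives: "Our objective is to determine the effect of and compare two different doses of IV dexamethasone given preoperatively before TKA", relative to placebo. This is tied to the outcome list that follows, which includes VAS pain, glucose, range of motion, SF-12 and KOOS, Jr.

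Statistical Analysis, sample size: "Assuming a mean difference in the VAS of 1.5 between placebo vs. low dose and 1.5 for low dose vs. high dose". The plan takes the difference between the two extreme arms as 3, and from these effects and a power of 90% it arrives at 47 in each arm, at least 141 overall.

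Statistical Analysis, model: a repeated-measures means model for VAS pain, range of motion, SF-12, KOOS, Jr. and glucose, with separate means by time and by "treatment group (dexamethasone or control". Two rules build on that factor: "T-tests will be used to compare the pairwise differences between the model-based treatment means (least-squares means) at each time point" and "Mean changes over time within a treatment group will be tested for linear trend". No other model, dose contrast or test of trend across doses appears in the document.

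**The concern.** The levels of the treatment factor decide which effects a means model can estimate. The model sentence is the only place where those levels are listed, and it lists two. That contradicts the three arms, the dose-comparison objective and the dose-by-dose sizing.

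An analyst who followed the sentence as written would report one dexamethasone-minus-control difference per time point and nothing by dose. The Introduction gives the unsettled choice of dose as a reason for the trial, and the pooled difference does not address it. The loss would extend to glucose, which is collected because hyperglycemia is a possible steroid complication. The within-group test of trend over time would also run on the two doses combined.

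If the text stays as it is, two analyses can claim to follow the plan, one pooled and one by arm. The choice between them could then be made after unblinding.

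**Working it through.** **Inputs**
- Arms: placebo, 10 mg, 20 mg (Study Design and Methods).
- Planned size: 47 per arm, 141 in total (Statistical Analysis).
- Assumed VAS differences: 1.5 for placebo vs low, 1.5 for low vs high, 3 for placebo vs high (Statistical Analysis).
- Two-sided tests at 0.05 (Statistical Analysis).
- SD of VAS: not given.

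**1. The plan's own figure.** 47 × 3 = 141 agrees. The 47 per arm cannot be confirmed without an SD. Solving n = 2(1.960 + 1.282)² SD² / d² for the SD, with n = 47 and d = 1.5, gives SD = 1.5 × √(47/2) / 3.242 ≈ 2.24. The figure is therefore consistent with a pairwise comparison of two arms at a difference of 1.5 if the SD is about 2.24. Other test choices imply other SDs: 2.49 for a one-sided 0.05 test, 1.98 for 0.05/3, and 4.04 for a three-group F test. Steps 2 to 4 need no SD.

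**2. Number of contrasts.** A factor with k levels gives k(k − 1)/2 pairwise differences per time point.
- k = 2: one, namely pooled dexamethasone (47 + 47 = 94) vs control (47).
- k = 3: three, namely 10 mg vs placebo, 20 mg vs placebo and 20 mg vs 10 mg.

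**3. What the single contrast would estimate.** With equal dose arms it is the average of the two dose effects: (47 × 1.5 + 47 × 3)/94 = 2.25.
- Against the assumed 10 mg effect: (2.25 − 1.5)/1.5 = +50%.
- Against the assumed 20 mg effect: (2.25 − 3)/3 = −25%.

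**4. Whether it can show a dose response.**

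| True effects (10 mg, 20 mg) | 20 mg vs 10 mg | Pooled contrast |
|---|---|---|
| (0, 3) | 3 | (0 + 3)/2 = 1.5 |
| (1.5, 1.5) | 0 | (1.5 + 1.5)/2 = 1.5 |

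The 20 mg vs 10 mg difference is not a function of the two-level model's parameters, so no contrast of its means recovers it. A noise-free least-squares fit with 47 per arm gives the same pooled coefficients: 2.25, 1.50 and 1.50 for dose effects (1.5, 3), (0, 3) and (1.5, 1.5).

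**5. Consistency with the sizing (SD assumed).** Normal-approximation power with 47 per arm, two-sided 0.05:

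| Assumed SD | Each 1.5 contrast, 47 vs 47 | Pooled 2.25, 47 vs 94 |
|---|---|---|
| 2.24 | 90.1% | >99.9% |
| 3 | 67.9% | 98.7% |
| 4 | 44.4% | 88.3% |

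At the SD where a 1.5 contrast has the planned 90% power, the pooled contrast has far more. If that is how 47 was reached, the trial was sized for the by-arm comparison and not for the pooled one.

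**The case against.** The strongest reply is that three groups were plainly meant. The model text never speaks of pooling or combining, and nothing else in the document proposes a pooled comparison. The sample-size paragraph, under the same heading, names all three VAS comparisons. The word pairwise fits three arms better than two. The protocol also uses two-group shorthand elsewhere for all three arms: "Both the intervention and control groups will receive spinal anesthesia" in Therapeutic Intervention, and a regimen entry that puts both doses under one study group. On this view the parenthesis names kinds of treatment and does not list factor levels.

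As evidence of intent, this stands. A reader might infer that the trial plans to merge its dose arms, and the documents do not support that. A reader might also infer that the dose comparison is prespecified nowhere. That goes too far as well, because the Objectives set it, against placebo and between doses, for every listed outcome. Nor are the dose effects lost for good: arm-level data will exist, so the by-arm analysis can still be run.

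The reply does not repair the model sentence. The pairwise tests are between the means of the factor just defined, and two levels make one pair. The shorthand in Therapeutic Intervention describes care common to all arms, where the number of groups changes nothing. In a model specification it decides what is estimated.

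**Conclusion.** The concern holds as a conflict between the model's treatment factor and the rest of the plan. It should be fixed, but it is recoverable. As literally specified, the model pools 94 dexamethasone patients against 47 controls and contains none of the three dose contrasts for any of the outcomes it covers.

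The mismatch in wording is certain. The analytic consequence depends on the sentence being followed literally, which was probably not intended. The 2.25, and its distances of +50% and −25% from the assumed dose effects, are therefore illustrations and not a forecast of error in the results. They assume equal arms, equal completeness and the plan's own effects of 1.5 and 3. That a two-level factor cannot separate (0, 3) from (1.5, 1.5) follows from equal dose arms alone and does not depend on the missing SD.

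**What to change.** In the model sentence of Statistical Analysis:

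- Replace the parenthesis with *placebo, 10 mg dexamethasone, 20 mg dexamethasone*, as a three-level factor with arm-by-time means.
- State that the pairwise differences are 10 mg vs placebo, 20 mg vs placebo and 20 mg vs 10 mg, for each modelled outcome.
- State that linear trend over time is tested within each of the three arms.

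This costs one line of wording and one model term, with no new data or patients. It should be made before treatment codes are released.

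It does not settle multiplicity. The plan gives only p < 0.05, and whether the three contrasts need joint error control should be decided separately.
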